Symptoms of CF often appear in infancy and childhood, the most frequent of which are respiratory symptoms, followed by failure to thrive, steatorrhea, and meconium ileus.^{1,3} The lungs of individuals with CF are colonized and infected by bacteria from an early age. This leads to chronic airway infection and inflammation, progressing to bronchiectasis, gas trapping, hypoxemia, and hypercarbia. Pulmonary insufficiency is responsible for 70.5% of CF-related deaths in the US.⁶ In the initial stage, common bacteria such as *Staphylococcus aureus* and *Haemophilus influenzae* colonize and infect the lungs. Eventually, *Pseudomonas aeruginosa* (and sometimes *Burkholderia cepacia*) dominates. Once within the lungs, these bacteria adapt to the environment and develop resistance to commonly used antibiotics.

Non-pulmonary complications of CF result from blockages of affected organs with thickened mucosal secretions. These blockages cause damage in the pancreas, liver, and intestines leading to exocrine pancreatic insufficiency, malabsorption, and recurrent pancreatitis; CF-related diabetes; chronic hepatobiliary disease and cirrhosis; and meconium ileus and distal intestinal obstructive syndrome.^{1,3} Male infertility due to azoospermia secondary to congenital absence of the vas deferens is also a common complication of CF.

Specific Aims

Approximately 11% of CF patients have premature termination codons (PTC), causing_truncated CFTR with little to no function. No approved therapies exist for patients with PTC mutations including W1282X, a unique mutation exhibiting partial CFTR activity even in its truncated form. CFTR modulators alone enhanced CFTR function in patient cells from W1282X/G542X CFTR. Several published studies including ours have shown CFTR modulators alone and/or in combination with readthrough (RT) agents benefit W1282X CFTR. Clinical studies further support an aspect of this notion, where two W1282X patients showed beneficial effect to Ivacaftor treatment. This sets the stage for studies to combine CFTR correctors, to improve truncated but partially active W1282X CFTR to the cell surface, with the CFTR potentiator ivacaftor.

Outcome Measures:

Change in Fev1

Participant Selection

Inclusion Criteria:

- 1. Evidence of singed and dated informed consent/assent documents indicating that the subject has been informed of all pertinent aspects of the trial
- 2. Age 18 years or older
- 3. Body weight > 16 kg.

- 4. Diagnosis of CF and documentation of the presence of a nonsense mutation of the CFTR gene, as determined by historical genotyping
- 5. Ability to perform a valid reproducible spirometry with FEV1 > 30% and < 90% predicted for age, gender, and height
- 6. If the subject is sexually active, willingness to abstain from sexual intercourse of employ a barrier or method of contraception during the study drug administration
- 7. Willingness and ability to comply with all study procedures and assessments.

Exclusion Criteria:

- 1. Any changes in a chronic treatment regimen for CF or for CF-related conditions within two weeks prior to screening
- 2. Evidence of pulmonary exacerbation or acute upper or lower respiratory tract infection within two weeks prior to screening.
- 3. Ongoing tobramycin immunosuppressive, warfarin, phenytoin, or tolbutamide therapy
- 4. History of solid organ or hematological transplantation.
- 5. A history of positive hepatitis B surface antigen test, hepatitis C antibody test, or human immunodeficiency
- 6. Major complications of lung disease within four weeks prior to screening
- 7. pregnancy or breast feeding
- 8. Current smoker or a smoking history of > 10 pack years
- 9. Prior or ongoing medical condition, medical history, physical findings, ECG, or laboratory abnormality that in the investigators opinion could adversely affect the safety of the subject, makes it unlikely that the course of treatment or follow-up would be completed or could impair the assessments of the study results

Recruitment Methods

Eligible participants will be recruited from the Principal Investigators Cystic Fibrosis specialty Care clinic the University of Alabama at Birmingham.

Study Methods:

This study will be an open-label, single-center study, where up to 5 CF patients homozygous for W1282X CFTR or W1282X mutation in-trans with other minimal function mutations will initiate Symdeko for 28 days followed by Ivacaftor for 28 days OR Ivacaftor for 28 days followed by a 28 day off period.

This assigned alternation will occur for 168 days for 9 study visits across a 6-month period.

Subjects may continue to receive existing therapy/prophylaxis for treatment of CF or CF-related conditions. The two treatment intervals will be summarized and evaluated for inter-individual and between treatment group analyses.

Statistical Analysis

Results will also be compared to historical run-in data already collected. Clinical efficacy of Symdeko as compared to baseline CFTR modulator therapy will be evaluated by lung function (spirometry).

Costs

The experimental procedure will be done at no cost to the subject or his/her insurance company. If any complications arise, they will be billed to the subject's insurance company.

Biostatistical Analysis

The within-subject change in FEV1 over baseline CFTR modulator therapy will be the primary efficacy outcome measure. Based on the design, the primary analysis will be a descriptive analysis of within-subject changes in outcome measures from week 1 to 24 of CFTR function. These data also will be used to test the null hypothesis of no change using the non-parametric Wilcoxon signed-rank test (due to small numbers). Change with washout (if conducted; this can be omitted for safety considerations) also will be informative. AE reporting will be conducted via listing tables and classified according to causality, per protocol. All statistical tests will be two-sided and will use α =0.05.

Risk and Discomforts

CFQR Questionnaire:

There is a possible risk of loss of confidentiality in questionnaires due to medical history not remaining private. This potential risk is guarded against by maintaining completed questionnaires in a locked filing system in a locked room at the Child Health Research Center and in password-protected computers located at the center.

Blood Draw

Drawing blood from the arm may cause pain, bruising, light-headedness, and, on rare occasions, infection.

Spirometry:

Some people may have some light-headedness or chest soreness from the hard blowing. The chest soreness usually goes away by itself. It can also be helped with non-prescription pain-relievers.

Sweat Test:

The Macroduct System is a frequently used system in hospitals and clinics worldwide. This is considered to be a very safe painless procedure, but rare small burns have been reported at the site of the electrode even though the participant showed no discomfort during the test.

Nasal Potential Difference Test:

Local irritation of the skin where the needle is placed and local infection at the site are possible but unlikely. Nasal irritation, tearing and sneezing may occur because of the tubing placement in the nose. Nose bleeding is possible, but very unlikely. Infusion of amiloride, isoproterenol and ATP into the nose will have no foreseeable risks or discomforts.

HNE Collection:

The brushings and/or scrapes inside the nose can be mildly painful and may be associated with a small amount of bleeding. The risk of infection at the site of the brushing and/or scrape is very small.

Rectal Biopsy:

The rectal biopsy will be mucosal and not transmural, acquiring approximately 2-3 mm of tissue

per biopsy from the very distal rectum (5 cm cephalad). Risks associated with the sub-study procedures include:

• Potential discomfort related to saline enema

• Potential risks of sedation- Conscious sedation will include use of intravenous midazolam and/or morphine as determined by the Gastroenterologist and based on UAB policies regarding conscious sedation (attached). Both medications may cause serious or life-threatening breathing problems such as shallow, slowed, or temporarily stopped breathing. This GI will monitor heart and lungs and to provide life-saving medical treatment quickly if needed.

- Potential risks of local bleeding and infection
- Very small risk of bowel perforation

Bleeding would be predicted to be self-limited and infection would be treatable with antibiotics.

Bowel perforation would be treated with antibiotics, repeat endoscopy and, in severe cases, with

surgical intervention. These risks are minimized by performing biopsies under direct visualization, not including subjects with diseased tissue in the distal rectum, and are small relative to the potential future benefits of developing new CF therapeutics to address patient specific CFTR mutation defects.

Risks of optional conscious sedation: Nausea and vomiting, although very uncommon, may occur. Slight risk of respiratory slowing and respiratory arrest

Risk will be minimized through continuous monitoring throughout participation in the study, including comprehensive laboratory assessments, and physical exams. Participants will undergo blood tests during this study to look for any possible changes in liver function > than 3X upper limit of normal and creatinine kinase.

Potential Benefits

There may be no direct medical benefits to the study participants. data acquired during the study may help inform how to treat people with cystic fibrosis in the future.

Monitoring and Quality Assurance

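### The primary FEV1 change is not tied to treatment blocks: read literally it ends on ivacaftor or off drug, and read loosely it leaves the tested change undefined

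*Combined protocol and SAP*

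**What the plan says.** Under Biostatistical Analysis the outcome is clear in kind: "The within-subject change in FEV1 over baseline CFTR modulator therapy will be the primary efficacy outcome measure". The Statistical Analysis section puts the question in terms of Symdeko against that same baseline, by spirometry.

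The primary analysis is then described as a "descriptive analysis of within-subject changes in outcome measures from week 1 to 24 of CFTR function", and the test follows from it: "These data also will be used to test the null hypothesis of no change using the non-parametric Wilcoxon signed-rank test". These are the only time points attached to the primary analysis.

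The schedule is under Study Methods. Participants "will initiate Symdeko for 28 days followed by Ivacaftor for 28 days OR Ivacaftor for 28 days followed by a 28 day off period", and the alternation runs for 168 days with 9 visits. No visit days are listed.

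Three other comparisons are mentioned, none with a visit or a baseline:

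- Study Methods: "The two treatment intervals will be summarized and evaluated for inter-individual and between treatment group analyses".
- Biostatistical Analysis: "Change with washout (if conducted; this can be omitted for safety considerations) also will be informative".
- Statistical Analysis: "Results will also be compared to historical run-in data already collected".

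**The concern.** The question is about Symdeko, but the stated time points do not select Symdeko values. A week 1 to week 24 change compares the start of the study with its last block, and Symdeko is never the last block.

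If the phrase is instead read as the length of the study, nothing says which FEV1 values make up each participant's change. A signed-rank test of no change needs exactly one such value per participant. In an open-label study that value could then be picked after the FEV1 data have been seen.

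The baseline is open in the same way. It could be the ivacaftor block, a pre-dose value or the run-in data, and these answer different questions. The sentence also speaks of CFTR function, while the primary outcome, here and under Outcome Measures, is FEV1.

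**Working it through.** **Calendar (from Study Methods).** 168/7 = 24 weeks, which matches the stated 24. 168/28 = 6 blocks. Block 6 is days 141-168 and week 24 is days 162-168, so all of week 24 lies in block 6.

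| Block order | Weeks 1-4 | 5-8 | 9-12 | 13-16 | 17-20 | 21-24 |
|---|---|---|---|---|---|---|
| Symdeko/ivacaftor pair repeated | Sym | Iva | Sym | Iva | Sym | Iva |
| Ivacaftor/off pair repeated | Iva | Off | Iva | Off | Iva | Off |
| Pairs alternate, Symdeko pair first | Sym | Iva | Iva | Off | Sym | Iva |
| Pairs alternate, ivacaftor pair first | Iva | Off | Sym | Iva | Iva | Off |

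Symdeko blocks end at weeks 4, 12 and 20 in the first order, never in the second, at weeks 4 and 20 in the third, and at week 12 in the fourth. Week 24 is ivacaftor or off drug in all four.

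**Weight of Symdeko in the literal change.** Define:

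- S and I: effects of Symdeko and ivacaftor over off drug;
- b: value at the start (0 if off drug, I if on ivacaftor);
- f: fraction of the first-block effect present at week 1 (0 if pre-dose);
- c: fraction of the difference S - I still present at the end of the next ivacaftor block.

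For the repeated Symdeko/ivacaftor pair:

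week 24 - week 1 = I + c(S - I) - [b + f(S - b)]

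The coefficient of S is c - f. With c = 0 it is zero (pre-dose week 1) or negative (on-treatment week 1). It is positive only if c exceeds f.

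**Illustration.** The documents give no effect sizes, so S = 6 and I = 2 are assumptions, in whatever FEV1 unit is chosen. Entries are for f = 0, 0.5, 1.

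| c | Literal change, off-drug start | Literal change, ivacaftor start | Block contrast (1 - c)(S - I) |
|---|---|---|---|
| 0 | +2, -1, -4 | 0, -2, -4 | +4 |
| 0.25 | +3, 0, -3 | +1, -1, -3 | +3 |
| 0.5 | +4, +1, -2 | +2, 0, -2 | +2 |

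With S = 5, I = 2 and c = 0, the literal change at f = 0 and f = 1 is +2 and -3 (off-drug start) or 0 and -3 (ivacaftor start), while S - I = +3. The +2 is the same for S = 5 and S = 6 because it is ivacaftor's effect alone.

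For the repeated ivacaftor/off pair with the off period taken, the change is 0 - [b + f(I - b)]. With I = 2 this is 0, -1, -2 (off-drug start) or -2, -2, -2 (ivacaftor start), and it contains no Symdeko term. If the off period is omitted, the documents do not say what those blocks contain.

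**Drift in the replacement contrast (repeated Symdeko/ivacaftor pair).** Under a linear trend:

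- Week 12 minus the mean of weeks 8 and 16: 12 - 12 = 0.
- Week 20 minus the mean of weeks 16 and 24: 20 - 20 = 0.
- Week 4 minus week 8: -4 weeks, or -1 block.
- Mean of the three: -1/3 block.

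A day 7 to day 168 change carries (168 - 7)/28 = 5.75 blocks of drift.

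**The case against.** The strongest reply is that week 1 to week 24 only names the study window. The stated question concerns Symdeko, changes is plural, and Study Methods plans summaries of the treatment intervals, so a period-based comparison is probably intended. That is a fair reading. But the interval summaries name no visit and no baseline and are not called primary, so this reading exchanges a misdirected contrast for an undefined one.

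Carryover also counts against a one-sided account. At c = 0.5 with an ivacaftor start and a pre-dose week 1, the literal change (+2) equals the block contrast (+2). The literal change is therefore not certain to lose Symdeko altogether.

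Three stronger inferences are tempting and are not supported:

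- A reader might infer that the primary analysis is bound to miss Symdeko. That needs both the literal reading and little carryover.
- A reader might infer that some participants never receive Symdeko, or that its blocks must end at weeks 4, 12 and 20. Both hold only if each participant repeats one pair three times. The reference to an assigned alternation favours this but does not state it.
- A reader might see a contradiction between the Specific Aims statement that no approved therapies exist for W1282X and the later reference to a baseline modulator. Lack of approval does not mean lack of use, and the same section reports two W1282X patients treated with ivacaftor. Ivacaftor is a plausible baseline; it is simply not named.

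Finally, the study is small and descriptive. That limits the stakes, but the descriptive contrast is then the study's main product.

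**Conclusion.** The point holds and should be fixed. That week 24 falls on ivacaftor or off drug follows from the stated block lengths under every order examined, taking off periods as given. On the literal reading, Symdeko's weight in the Symdeko/ivacaftor sequence is c - f: zero or negative without carryover, and positive only when carryover exceeds the response already present at week 1. On the window reading, the primary change and its baseline are undefined. Neither reading gives a pre-stated Symdeko contrast.

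The sign argument does not depend on the assumed effects; the sizes shown do. With at most 5 participants and a descriptive primary analysis, the consequence is a misdirected or unclear primary summary and not a wrong confirmatory decision.

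**What to change.** Replace the week 1 to week 24 wording, including its reference to CFTR function, with one FEV1 contrast per participant in one stated unit:

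1. **Primary.** The mean over a participant's Symdeko blocks of end-of-Symdeko-block FEV1 minus end-of-ivacaftor-block FEV1. Where ivacaftor blocks lie immediately on both sides of a Symdeko block, subtract their average, which cancels linear drift for that block. Use the weeks that the assigned sequence gives: Symdeko ends at weeks 4, 12 and 20 if the Symdeko/ivacaftor pair is repeated three times.
2. **Baseline.** If the sponsor means a pre-dose or run-in value, name it before analysis, subtract it instead, and report the Symdeko-ivacaftor difference as secondary.
3. **Ivacaftor versus off.** Report separately, using only cycles in which the off period took place.
4. **Week 1 to week 24.** Keep as a descriptive trend.

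The cost is SAP wording plus spirometry at block ends. Six block ends and one pre-dose visit use 7 of the 9 planned visits, and no treatment schedule changes. The downsides are that fewer participants may contribute to the Symdeko estimate, missed block-end visits lose cycles, and carryover into the ivacaftor block shrinks the difference by the fraction c. A Symdeko block without ivacaftor on both sides keeps one block of drift. With a pre-dose baseline and Symdeko ends at weeks 4, 12 and 20, the mean gap is (28 + 84 + 140)/3 = 84 days, or three blocks of drift. With run-in data the gap is unknown because no dates are given.

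### With at most 5 participants, the exact two-sided Wilcoxon signed-rank test cannot reach p<0.05, and the plan does not say whether the p-value is exact or approximate

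*Combined protocol and SAP*

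**What the plan says.** The Study Methods section enrols "up to 5 CF patients homozygous for W1282X CFTR or W1282X mutation in-trans with other minimal function mutations" and states no minimum number. On follow-up it says: "This assigned alternation will occur for 168 days for 9 study visits across a 6-month period".

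The Biostatistical Analysis section defines the outcome: "The within-subject change in FEV1 over baseline CFTR modulator therapy will be the primary efficacy outcome measure". It then says that "the primary analysis will be a descriptive analysis of within-subject changes in outcome measures from week 1 to 24 of CFTR function". The same data are also to be used to "test the null hypothesis of no change using the non-parametric Wilcoxon signed-rank test (due to small numbers"). The section ends: "All statistical tests will be two-sided and will use α =0.05".

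The plan does not say whether the p-value is exact or from a normal approximation, whether a continuity correction applies, how zero or tied changes are handled, or which visits form each participant's change. It names no other hypothesis test and gives no power or sample size calculation.

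**The concern.** The plan chooses a non-parametric test because the sample is small, but the sample is too small for that test to reject at the stated level. The signed-rank test has a discrete null distribution. With five or fewer values, even the most extreme possible result has an exact two-sided p-value above 0.05.

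Two things follow. First, if the test is computed exactly, its result is known before any data are collected, and a reader could take an inevitable p>0.05 as evidence of no effect even if every participant improved. Second, because the version is not specified, the most favourable result at n=5 can be significant or not depending on a software setting. In an open-label study that choice could be made after the data are seen.

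**Working it through.** **Inputs.** At most n=5 participants (Study Methods). Wilcoxon signed-rank test, two-sided, α=0.05 (Biostatistical Analysis). One non-zero change per participant is an assumption, since the plan does not say which visit values enter the test. There is no power or sample size figure in the plan to reproduce.

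**Exact test.** Under the null, the 2^n assignments of signs to the ranked changes are equally likely. The two most extreme are all positive and all negative, so the smallest two-sided p is 2/2^n:

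- n=5: 2/32 = 0.0625
- n=4: 2/16 = 0.125
- n=3: 2/8 = 0.25
- n=6, for comparison: 2/64 = 0.03125

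At least 6 non-zero changes are needed before the exact test can reject at 0.05. Tied magnitudes alter the ranks but not this floor. Enumerating every tie pattern for n=3, 4 and 5 gave the same minimum and no rejections. A zero change, if dropped, lowers n and raises the floor.

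**Normal approximation, n=5, no ties.** When all changes are positive, W=15. The mean is n(n+1)/4 = 7.5, the variance is n(n+1)(2n+1)/24 = 13.75, and the SD is 3.708.

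- Uncorrected: z = 7.5/3.708 = 2.023, p = 0.043, which rejects.
- Continuity-corrected: z = 7.0/3.708 = 1.888, p = 0.059, which does not reject.

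The next most extreme value of W gives an uncorrected p of 0.080. The uncorrected rule therefore rejects only when all five signs agree. Its type I error is 2/32 = 6.25%, which is 1.25 percentage points above the stated 5%.

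**Ties in the approximation.** The variance falls by the sum of (t³−t)/48 over groups of t tied values. For five equal magnitudes it is 13.75 − 120/48 = 11.25, giving p = 0.025 uncorrected and 0.037 corrected. For four equal magnitudes at n=4 it is 7.5 − 60/48 = 6.25, so z = 5/2.5 = 2.0 and p = 0.0455 uncorrected.

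Smallest attainable two-sided p:

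| n | Exact | Uncorrected, untied | Corrected, untied | Uncorrected, all equal | Corrected, all equal |
|---|---|---|---|---|---|
| 5 | 0.0625 | 0.043 | 0.059 | 0.025 | 0.037 |
| 4 | 0.125 | 0.068 | 0.100 | 0.0455 | 0.072 |
| 3 | 0.25 | 0.109 | 0.181 | 0.083 | 0.149 |

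Wherever an approximation rejects, all changes share a sign. Its true type I error is then 6.25% at n=5, or 2/16 = 12.5% in the single rejecting case at n=4.

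**The case against.** The strongest reply is that little depends on this test. The primary analysis is descriptive, there is no success criterion or go/no-go rule, and the study is small, open-label and single-centre. That is correct and limits the point to how the test is specified and reported. It does not remove the point, because this is the only test the plan names and a significance level is attached to it.

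A second reply is that the tied-magnitude results are remote. Four or five identical FEV1 changes are unlikely, so the 12.5% figure is a corner case. The untied n=5 result is the one that matters in practice.

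A third reply is that the 9 visits supply more than five values. Alternating 28-day periods over 168 days make 168/56 = 3 cycles, so up to 5×3 = 15 differences between adjacent periods. These could be treated as independent under a null of no effect in any participant, with no carryover, trend or serial correlation. Those assumptions are strong and the plan does not make them. Such differences are also not the stated outcome, which is change over baseline. Several changes from one participant against a shared baseline are not independent, so pooling them does not validly lower the floor.

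Finally, a one-sided exact test could reach 1/32 = 0.03125 at n=5, but the plan specifies two-sided tests.

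**Conclusion.** The concern holds. With one change per participant and at most 5 participants, the exact two-sided test has 0% power at α=0.05 for any effect on FEV1 or any other outcome to which it is applied. If the uncorrected approximation is used instead with five untied changes, the test can reject, but its type I error is 6.25%. The plan does not say which version applies.

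The conclusion depends on one value per participant, which is the natural reading of a change per person but is not stated. The exact floor holds with or without ties. The approximate p-values do depend on ties. The descriptive primary analysis stands as written. The defect is worth correcting because it is certain before any data are collected and the repair is small.

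**What to change.** Either delete the Wilcoxon test and rely on the descriptive analysis, or replace its sentence with wording such as:

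> A supplementary exact two-sided Wilcoxon signed-rank test will be reported, using one value per participant. With n non-zero changes the smallest attainable p-value is 2/2^n: 0.0625 for 5 participants, 0.125 for 4 and 0.25 for 3. No significance decision will be made, and p>0.05 will not be read as absence of effect.

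The plan should also name the visits that form each participant's value. The sentence setting α=0.05 should be deleted or limited to any other tests that are run. Limiting it is safer, because the plan also mentions comparisons between treatment groups and with earlier run-in data. Any tests used there would otherwise have no stated level or sidedness.

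The cost is a few sentences in the analysis section, with no change to design or data collection. The study gives up a formal significance statement, which the exact test could not have delivered.
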